1.3. Summary of Clinical Data

1.3.1. Pharmacokinetics and Product Metabolism

Following oral administration of ibrutinib at doses ranging from 420 to 840 mg/day, exposure to ibrutinib increased proportionally with substantial intersubject variability. The mean terminal plasma elimination half life ($t_{1/2}$) of ibrutinib ranged from 4 to 13 hours, with a median time to maximum plasma concentration (T_{max}) of 2 hours. Despite the doubling in mean systemic exposure when dosed with food, the favorable safety profile of ibrutinib allows dosing with or without food. Ibrutinib is extensively metabolized primarily by cytochrome P450 (CYP) 3A4. The on-target effects of the main metabolite PCI-45227 are not considered clinically relevant. Steady-state exposure of ibrutinib and PCI-45227 was less than 2-fold of first dose exposure implying non-clinically relevant accumulation. Less than 1% of ibrutinib is excreted in the urine. Ibrutinib exposure is not altered in patients with creatinine clearance (CrCl) >30 mL/min. Patients with severe renal impairment or patients on dialysis have not been studied. Following single dose administration, the AUC of ibrutinib increased 2.7-, 8.2- and 9.8-fold in subjects with mild (Child-Pugh class A), moderate (Child-Pugh class B), and severe (Child-Pugh class C) hepatic impairment compared to subjects with normal liver function. A higher proportion of Grade 3 or higher adverse reactions were reported in patients with B-cell malignancies (CLL, MCL and WM) with mild hepatic impairment based on NCI organ dysfunction working group (NCI-ODWG) criteria for hepatic dysfunction compared to patients with normal hepatic function.

For the most comprehensive information regarding pharmacokinetics (PK) and product metabolism, please refer to the current version of the [IB](#).

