13. Currently active clinically significant cardiovascular disease such as uncontrolled arrhythmia, congestive heart failure, any Class 3 or 4 cardiac disease as defined by the New York Heart Association Functional Classification ([Appendix J](#)), or history of myocardial infarction within 6 months prior to first dose with study drug
14. Unable to swallow capsules or disease significantly affecting gastrointestinal function and/or inhibiting small intestine absorption such as; malabsorption syndrome, resection of the small bowel, or poorly controlled inflammatory bowel disease affecting the small intestine
15. Uncontrolled active systemic fungal, bacterial, viral, or other infection (defined as exhibiting ongoing signs/symptoms related to the infection and without improvement, despite appropriate antibiotics or other treatment) or ongoing intravenous anti-infective treatment
16. Known history of infection with human immunodeficiency virus (HIV)
17. Serologic status reflecting active hepatitis B or C infection. Patients with hepatitis B core antibody positive who are surface antigen negative or who are hepatitis C antibody positive will need to have a negative polymerase chain reaction (PCR) result prior to enrollment. Those who are hepatitis B surface antigen positive or hepatitis B PCR positive and those who are hepatitis C PCR positive will be excluded.
18. History of stroke or intracranial hemorrhage within 6 months prior to randomization.
19. Pregnant or lactating women
20. Current life-threatening illness, medical condition, or organ system dysfunction which, in the Investigator's opinion, could compromise the patient's safety or put the study at risk
21. Requires or receiving anticoagulation with warfarin or equivalent vitamin K antagonists (eg, phenprocoumon) within 28 days of first dose of study drug
22. Requires treatment with a strong CYP3A4/5 inhibitor

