6.6.1.1. Guideline for Use of CYP Inhibiting/Inducing Drugs

Ibrutinib is metabolized primarily by CYP3A4. Avoid co-administration with strong or moderate CYP3A inhibitors and consider alternative agents with less CYP3A inhibition. Co-administration of ketoconazole, a strong CYP3A inhibitor, in 18 healthy subjects increased dose normalized exposure, C_{max} and AUC_{0-last} , of ibrutinib by 29- and 24-fold, respectively. The maximal observed ibrutinib exposure (AUC) was ≤ 2 -fold in 37 patients treated with mild and/or moderate CYP3A inhibitors when compared with the ibrutinib exposure in 76 patients not treated concomitantly with CYP3A inhibitors. Clinical safety data in 66 patients treated with moderate (n=47) or strong CYP3A inhibitors (n=19) did not reveal meaningful increases in toxicities. Strong inhibitors of CYP3A (eg, ketoconazole, indinavir, nelfinavir, ritonavir, saquinavir, clarithromycin, telithromycin, itraconazole, and nefazadone) should be avoided. If a strong CYP3A inhibitor must be used, consider reducing the ibrutinib to 140 mg or withhold treatment temporarily. Subjects should be monitored for signs of ibrutinib toxicity. If the benefit outweighs the risk and a moderate CYP3A inhibitor must be used, reduce ibrutinib to 140 mg for

the duration of the inhibitor use. Monitor subject for toxicity and follow dose modification guidance as needed. For subjects who are already on a moderate CYP3A inhibitor concomitantly with ibrutinib without significant toxicity the investigator may consider the overall risk-benefit to determine if a dose reduction of ibrutinib is appropriate. Avoid grapefruit and Seville oranges during ibrutinib treatment, as these contain moderate inhibitors of CYP3A (see [Section 6.2.1](#)). No dose adjustment is required in combination with weak CYP3A inhibitors.

Co-administration of ibrutinib with strong CYP3A inducer, rifampin, in healthy subjects decrease ibrutinib plasma concentration by approximately 10-fold. Avoid concomitant use of strong CYP3A inducers (eg, carbamazepine, rifampin, phenytoin, and St. John's Wort). Consider alternative agents with less CYP3A induction.

A list of common CYP3A inhibitors and inducers is provided in [Appendix C](#); a comprehensive list of inhibitors, inducers, and substrates may be found at <http://medicine.iupui.edu/clinpharm/ddis/main-table/>. This website is continually revised and should be checked frequently for updates.

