6.6.2. Prohibited Concomitant Medications

Any chemotherapy, anticancer immunotherapy, corticosteroids (at dosages equivalent to prednisone >20 mg/day), experimental therapy, or radiotherapy are prohibited. Localized, hormonal, or bone sparing treatment for non-B cell malignancies may be considered with approval of the medical monitor. Steroids used to premedicate or manage ofatumumab infusion-related reactions or contrast allergies are permitted. In addition, short courses (<14 days) of treatment for non-cancer related medical reasons (treatment for autoimmune cytopenias are permitted) at doses not to exceed 100 mg/day of prednisone or equivalent are permitted. Routine infusion premedication with corticosteroid doses of >100 mg IV prednisolone (or equivalent) is not permitted. Red blood cell growth factors (eg, erythropoietin), platelet growth factors (eg, thrombopoietin) and sargramostim are also prohibited for the first six months of study treatment. However, initiation of red blood cell growth factors (eg, erythropoietin), platelet growth factors (eg, thrombopoietin) and/or sargramostim can be considered after 6 months on study based on the indication outlined in the respective package inserts.

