Appendix C: Inhibitors and Inducers of CYP3A

Inhibitors of CYP3A are defined as follows. A comprehensive list of inhibitors can be found at the following website: <http://medicine.iupui.edu/clinpharm/ddis/main-table/>. The general categorization into strong, moderate, and weak inhibitors according to the website is displayed below. Refer to [Section 6.6.1.1](#) on instructions for concomitant use of CYP3A inhibitors or inducers with ibrutinib.

Inhibitors of CYP3A	Inducers of CYP3A

Strong inhibitors: indinavir nelfinavir ritonavir clarithromycin itraconazole ketoconazole nefazodone saquinavir suboxone telithromycin cobicistat boceprevir mibefradil telaprevir troleandomycin posaconazole ^a
 
Moderate inhibitors: aprepitant amprenavir amiodarone atazanavir ciprofloxacin crizotinib darunavir/ritonavir dronedarone erythromycin diltiazem fluconazole grapefruit juice Seville orange juice verapamil voriconazole ^b imatinib
 
Weak inhibitors: cimetidine fluvoxamine
 
All other inhibitors: chloramphenicol delavirdine diethyl-dithiocarbamate mifepristone norfloxacin norfluoxetine star fruit
	
carbamazepine efavirenz nevirapine barbiturates glucocorticoids modafinil oxcarbazepine phenobarbital phenytoin pioglitazone rifabutin rifampin St. John’s Wort troglitazone

Source: <http://medicine.iupui.edu/clinpharm/ddis/main-table/>

- a. Based on PBPK simulations, up to 9.7-fold increase in AUC and 6.2-fold increase in C_{max} could be observed. If ibrutinib needs to be administered with posaconazole, 140 mg ibrutinib will be dosed.
- b. Based on internal data, 140 mg ibrutinib dosed with voriconazole produces ibrutinib exposures similar to 560 mg ibrutinib dosed alone. Therefore, for this study, if ibrutinib needs to be administered with voriconazole, 140 mg ibrutinib will be dosed.

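### Section 6.6.1.1 leaves unclear whether ibrutinib must be reduced or held with a strong CYP3A inhibitor, though it plainly requires 140 mg with a newly started moderate one

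*Protocol*

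**What the plan says.** Protocol Section 6.6.1.1 first advises against both strong and moderate CYP3A inhibitors. It then covers the cases where one cannot be avoided:

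- Strong inhibitor: "If a strong CYP3A inhibitor must be used, consider reducing the ibrutinib to 140 mg or withhold treatment temporarily", with monitoring for toxicity.
- Moderate inhibitor, newly needed: if "a moderate CYP3A inhibitor must be used, reduce ibrutinib to 140 mg for" as long as the inhibitor is used.
- Moderate inhibitor already being taken without significant toxicity: reduction is left to the investigator's judgement.

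The same section reports that ketoconazole, a strong inhibitor, raised dose-normalized Cmax and AUC "of ibrutinib by 29- and 24-fold, respectively" in 18 healthy subjects. The largest AUC increase in 37 patients on mild or moderate inhibitors was at most 2-fold.

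Appendix C, to which Section 6.6.1.1 refers, lists 16 strong inhibitors. Footnote a fixes the dose for one of them: "If ibrutinib needs to be administered with posaconazole, 140 mg ibrutinib will be dosed". Footnote b fixes 140 mg for voriconazole, which the appendix classes as moderate, because "140 mg ibrutinib dosed with voriconazole produces ibrutinib exposures similar to 560 mg ibrutinib dosed alone".

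Section 6.6.2 does not name CYP3A inhibitors in its prohibited list (the opening list ends "experimental therapy, or radiotherapy are prohibited"). The mandatory discontinuation in Section 10.1 for needing prohibited treatment is therefore not triggered. Exclusion 22 in Section 5.2 ("Requires treatment with a strong CYP3A4/5 inhibitor") applies at randomization. None of the 11 next-line criteria in Section 7.3.4.1 mentions CYP3A.

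**The concern.** The sentence on strong inhibitors is governed by a soft verb, while the sentence on moderate inhibitors is an order. The firmer instruction is thus attached to the smaller interaction. If the soft verb covers both options, no dose action is required for 15 of the 16 listed strong inhibitors, and a patient could stay on 420 mg with the site fully compliant.

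What is at stake is the safety of patients taking ibrutinib, including ofatumumab patients who cross over. The protocol does not treat the situation as impossible. Section 7.1.21 and footnote d of Appendix M both plan PK sampling for patients who have to take strong or moderate inhibitors, but neither gives a dose.

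**Working it through.** There is no design figure to reproduce. The check is a comparison of texts, plus arithmetic to show scale.

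**Step 1: the two readings.** Read as reduce or else withhold, the sentence bars 420 mg. Read as consider either, it requires nothing. No other section settles it. Section 6.6.2 is silent, Appendix C settles posaconazole only (16 − 1 = 15 left open), and Sections 7.1.21 and Appendix M footnote d only collect samples.

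**Step 2: exposure.** Formula: AUC relative to 420 mg alone = fold increase × dose / 420. This assumes dose proportionality. Section 1.3.1 says that "exposure to ibrutinib increased proportionally with substantial intersubject variability", but only for 420 to 840 mg, so extending it down to 140 mg is an assumption.

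Inputs are 24-fold for ketoconazole and at most 2-fold for mild or moderate agents pooled (Section 6.6.1.1), and up to 9.7-fold for posaconazole, simulated (Appendix C footnote a). For voriconazole, footnote b implies 560/140 = 4.0-fold.

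| Inhibitor | Ibrutinib dose | Relative AUC |
|---|---|---|
| Ketoconazole (strong) | 420 mg, if continued | 24 × 420/420 = 24 |
| Ketoconazole (strong) | 140 mg | 24 × 140/420 = 8.0 |
| Posaconazole (strong) | 140 mg, required | 9.7 × 140/420 = 3.2 |
| Voriconazole (moderate) | 140 mg, required | 4.0 × 140/420 = 1.3 |
| Mild/moderate, pooled maximum | 140 mg | 2 × 140/420 = 0.67 |

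Even against voriconazole, the strong interactions are larger: 24/4.0 = 6.0 times for ketoconazole and 9.7/4.0 = 2.4 times for posaconazole. The documents give exposure figures for only these two strong inhibitors. If the other 14 lie between them (an assumption), continuing 420 mg would mean about 9.7 to 24 times the reference AUC, and 140 mg about 3.2 to 8.0 times.

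**Step 3: how the protocol treats comparable exposure elsewhere.** Section 1.3.1 gives AUC increases of 2.7-, 8.2- and 9.8-fold in mild, moderate and severe hepatic impairment. Section 6.2.6 responds as follows:

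- Mild: recommended 280 mg, so 2.7 × 280/420 = 1.8 times.
- Moderate: recommended 140 mg, so 8.2 × 140/420 = 2.7 times.
- Severe: study drug must be held until impairment improves to moderate or better.

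So at about 3- to 10-fold the protocol recommends or requires a lower dose or a hold. At 24-fold its wording leaves the action unclear.

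**Step 4: do the other safeguards cap the dose?**

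- Avoidance advice (6.6.1.1) does not govern the case where the inhibitor is unavoidable.
- Toxicity monitoring, and the holds and reductions in 6.2.2 and 6.2.4, act after toxicity appears.
- PK sampling (7.1.21, Appendix M footnote d) measures exposure without limiting it.
- Medical Monitor approval (7.3.4.1, criterion 1) covers entry to next-line ibrutinib, not an inhibitor started later.

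None states a maximum dose.

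**The case against.** **The stricter reading is plausible.** The verb for withholding is a bare imperative. The sentence follows two pieces of avoidance advice, names two actions and does not offer continued 420 mg as a third. This stands. A reader might infer that the protocol permits 420 mg with a strong inhibitor, but the documents support only that it fails to exclude it clearly.

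**No harm is shown.** Section 6.6.1.1 reports no meaningful rise in toxicity among 66 patients on moderate or strong inhibitors. This also stands, so an inference that patients were harmed has no support. The reassurance is thin, however: only 19 were on strong inhibitors, and their ibrutinib doses are not given.

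**The 24-fold figure and the count of 15 overstate practical exposure.** The figure is one inhibitor in healthy subjects. Several listed drugs are HIV agents, and known HIV infection was an exclusion at entry. Both points are fair. The documents do not say how often strong inhibitors are used.

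**140 mg is not clearly safe either.** With ketoconazole it gives 8 times the reference AUC, twice that of unreduced 420 mg with voriconazole (4 times). Correct. A 140 mg ceiling limits exposure without normalizing it, and that is why withholding must remain an equal option.

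**The next-line criteria.** A reader might see the missing counterpart to exclusion 22 as a serious gap, since criterion 8 of Section 7.3.4.1 does carry over the warfarin exclusion. The documents do not bear that out. Section 7.3.4.1 is looser than Section 5 in several respects (ECOG up to 3, platelets from 25,000/µL), Medical Monitor approval is its first criterion, concomitant medications are recorded at the next-line assessment, and Appendix M foresees strong-inhibitor use.

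**Conclusion.** The point holds as an ambiguity in a dosing-safety rule. Section 6.6.1.1 does not make clear that any ibrutinib action is mandatory with a strong inhibitor, while it does so for a newly started moderate one, and only posaconazole among the 16 listed strong inhibitors has a binding dose. On the permissive reading the exposure at issue is up to about 24 times the AUC of 420 mg alone. A 140 mg ceiling would bring that to about 8 times. The 24 is the high end from one small healthy-subject study, and the 8 also rests on dose proportionality below 420 mg.

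Priority is low to moderate. The number of patients affected is unknown and probably small at this stage: the SAP works from a final data extract of 26 November 2018, and patients still on treatment at closure may move to a separate extension study. Nothing here affects the PFS result.

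**What to change.** In Section 6.6.1.1, replace the sentence on strong inhibitors with:

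*If a strong CYP3A inhibitor must be used, withhold ibrutinib temporarily or reduce it to 140 mg for the duration of inhibitor use, with toxicity monitoring; do not continue above 140 mg; follow Appendix C where it gives a dose.*

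The rule on moderate inhibitors can stay as it is. Optionally, add to Section 7.3.4.1 a criterion that the patient does not need a strong CYP3A4/5 inhibitor when next-line ibrutinib starts, unless the Medical Monitor approves dosing under Section 6.6.1.1 and Appendix C. This would mainly prompt the question during an approval that is already required.

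The cost is one sentence in an amendment (two with the optional criterion), with no new data or patients. The downside is less investigator discretion and some dose interruptions. Keeping the 140 mg option matters because a long hold is a real cost in relapsed disease.

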6.6.1.2. Drugs That May Have Their Plasma Concentrations Altered by Ibrutinib

In vitro studies indicated that ibrutinib is not a substrate of P-glycoprotein (P-gp), but is a mild inhibitor (with an IC_{50} of 2.15 $\mu\text{g/mL}$). Ibrutinib is not expected to have systemic drug-drug interactions with P-gp substrates. However, it cannot be excluded that ibrutinib could inhibit intestinal P-gp after a therapeutic dose. Currently, no clinical data is available; therefore, co-administration of narrow therapeutic index P-gp substrates (eg, digoxin) with ibrutinib may increase the substrate's blood concentration and should be used with caution and subjects should be monitored closely for toxicity.

6.6.1.3. Concomitant Use of QT Prolonging Agents

Any medications known to cause QT prolongation should be used with caution; periodic monitoring with electrocardiograms and electrolytes should be considered.

6.6.1.4. Concomitant Use of Antiplatelet Agents and Anticoagulants

Warfarin or vitamin K antagonists should not be administered concomitantly with ibrutinib. Ibrutinib should be used with caution in patients requiring other anticoagulants or medications that inhibit platelet function. Supplements such as fish oil and vitamin E preparations should be avoided. Subjects with congenital bleeding diathesis have not been studied. For guidance on ibrutinib and the use of anticoagulants during procedures/surgeries see [Section 6.6.3](#).

Patients requiring the initiation of therapeutic anticoagulation therapy (eg, atrial fibrillation), consider the risks and benefits of continuing ibrutinib treatment. If therapeutic anticoagulation is clinically indicated, treatment with ibrutinib should be held and not be restarted until the patient

is clinically stable and has no signs of bleeding. Patients should be observed closely for signs and symptoms of bleeding. No dose reduction is required when study drug is restarted.

6.6.2. Prohibited Concomitant Medications

Any chemotherapy, anticancer immunotherapy, corticosteroids (at dosages equivalent to prednisone >20 mg/day), experimental therapy, or radiotherapy are prohibited. Localized, hormonal, or bone sparing treatment for non-B cell malignancies may be considered with approval of the medical monitor. Steroids used to premedicate or manage ofatumumab infusion-related reactions or contrast allergies are permitted. In addition, short courses (<14 days) of treatment for non-cancer related medical reasons (treatment for autoimmune cytopenias are permitted) at doses not to exceed 100 mg/day of prednisone or equivalent are permitted. Routine infusion premedication with corticosteroid doses of >100 mg IV prednisolone (or equivalent) is not permitted. Red blood cell growth factors (eg, erythropoietin), platelet growth factors (eg, thrombopoietin) and sargramostim are also prohibited for the first six months of study treatment. However, initiation of red blood cell growth factors (eg, erythropoietin), platelet growth factors (eg, thrombopoietin) and/or sargramostim can be considered after 6 months on study based on the indication outlined in the respective package inserts.

6.6.3. Guidelines for Ibrutinib Management with Surgeries or Procedures

Ibrutinib may increase risk of bleeding with invasive procedures or surgery. The following guidance should be applied during the perioperative period for subjects who require surgical intervention or an invasive procedure while receiving ibrutinib:

- For any surgery or invasive procedure requiring sutures or staples for closure, ibrutinib should be held at least 7 days prior to the intervention and should be held at least 7 days after the procedure and restarted at the discretion of the investigator when the surgical site is reasonably healed without serosanguineous drainage or the need for drainage tubes.
- For minor procedures (such as a central line placement, needle biopsy, thoracentesis, or paracentesis) ibrutinib should be held for at least 3 days prior to the procedure and should not be restarted for at least 3 days after the procedure. For bone marrow biopsies that are performed while the subject is on ibrutinib, it is not necessary to hold ibrutinib for these procedures.
- For emergency procedures, ibrutinib should be held after the procedure until the surgical site is reasonably healed, for at least 7 days after the urgent surgical procedure.

7. EFFICACY AND SAFETY PROCEDURES

The Schedule of Assessments is provided in [Appendix A](#). Descriptions of the scheduled evaluations are outlined below.

Before study entry, throughout the study, and at the follow-up evaluations, various clinical and diagnostic laboratory evaluations are outlined. The purpose of obtaining these detailed measurements is to ensure adequate safety and efficacy assessments. Clinical evaluations and laboratory assessments may be repeated more frequently if clinically indicated.

7.1. Description of Procedures

7.1.1. Informed Consent

The patient must read, understand, and sign the Institutional Review Board/Research Ethics Board/Independent Ethics Committee (IRB/REB/IEC)-approved informed consent form (ICF) confirming his or her willingness to participate in this study before any study-specific screening procedures are performed. Patients must also grant permission to use protected health information per Health Insurance Portability and Accountability Act (HIPAA). In addition, patients must sign all approved ICF amendments per the site IRB/REC/IEC's guidelines during the course of the study.

7.1.2. Confirmation of Eligibility

Perform all necessary procedures and evaluations to document that the patient meets each eligibility criterion ([Section 5](#)). Please refer to the study manual for a more detailed description of the enrollment procedures. Blood samples for hematology, coagulation, and serum chemistry collected at Screening will be evaluated by a central laboratory to confirm eligibility. If central labs submitted during the screening period are unable to be resulted (eg, specimen clotted or hemolysis) to support eligibility, the Medical Monitor may review local labs and approve the patient for randomization based on these lab values on a case by case basis provided another sample is redrawn and submitted prior to treatment.

